2.3.2 Assignment to intervention group A or control group B

- Patients will be randomized using a permuted block method to receive one of two possible intervention strategies A or B.
- The permuted block technique aims to ensure a periodic balance in the number of subjects assigned to each intervention or control group (Molina et al., 2015).
- The random assignment sequence will be generated by technical staff of the project with the support of a statistician.

Intervention Group A: This intervention involves utilizing a pictogram system named SIMAP (Automatic Association System of Medical Instructions to Pictograms), which was developed during the initial phase of the study. In essence, SIMAP comprises a series of pictograms intended to enhance the understanding of medical instructions provided by the healthcare team regarding asthma management. The pictograms will be designed by a panel of experts, as detailed in the previous sections of the project, and validated among adult patients consulting in the same population where this study will be implemented. The designed pictograms are specifically tailored to certain elements within the management of bronchial asthma.

This intervention entails furnishing the patient with the instruction sheet given by the clinical staff of the CESFAM as part of their care, but supplemented with pictograms (automatically generated by SIMAP). The provided instructions include images supporting guidance for recognizing bronchodilators, indicating their method of use (daily dose, usage schedule, or as needed), specifications of bronchodilator families with their functions (disease-controlling and symptom-relieving drugs), inhalation technique of bronchodilators, and the use of an inhalation chamber in the process.

The pictograms will be administered by the clinical professional of the CESFAM designated by the Director or by the clinical professional hired by the project (recruiter). This depends on the care process of the CESFAM participating in this study and the availability of hours of the clinical professional of the CESFAM designated by the Director to support the project.

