3.1. Outcomes

The primary outcome of the study consists of the difference in disease control level 60 days after the start of the study, as assessed by the ACT questionnaire. As co-primary outcomes, the same score difference observed at 7 and 30 days after the intervention has been established, as well as adherence to the recommendations provided by the healthcare team regarding the correct inhalation technique for bronchodilators and the use of inhalation chambers within the same time frames. Secondary outcomes of the study include the recognition of the function of bronchodilators. To check adherence to the correct application of the inhalation technique, the project clinician will conduct an assessment of the correct use of the prescribed inhalation therapy according to a checklist developed 10 months after the start of the project. The checklist was developed following the recommendations of national clinical guidelines, the Spanish Association of Pediatrics in Primary Care, and a study conducted by Santo Tomás University on inhalation techniques in asthmatic patients (Manríquez et al., 2015).ris

Additionally, secondary outcomes will include the occurrence of urgent care visits, hospitalizations related to the disease, and the need to escalate bronchodilator therapy as per GINA guidelines at 60 days. Information regarding these secondary outcomes will be extracted from the individual medical records of each patient, as well as during the final follow-up interview when the ACT questionnaire is administered.

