3.2. Sample Size

In this stage, we will be working with new patients entering the ARU. Based on the actual population size of adult patients with bronchial asthma recorded from 2019 to 2021 in the participating centers of the project, we have considered a minimum sample size of 48 patients, with a 10% margin of error and a 95% confidence level. We anticipate recruiting this sample within a period of no more than 6 months from the entry of the first patient. The sample calculation takes into account the years during which the COVID-19 social and health crisis occurred. Additionally, due to the lack of previous literature on the evaluation of pictograms for asthma control, it is not feasible to calculate a sample size based on the effect size to be achieved. Ideally, we aim for a homogeneous sample according to the a priori population of entries for each participating center. However, in case of recruitment difficulties at any health center, the sample will be obtained based on the center with the highest availability of patient entries that meet the selection criteria. Considering the measurement of the primary and co-primary outcomes, we plan to randomize a minimum of 48 patients for Stage 2 of the clinical validation of SIMAP.

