3.4. Analysis Strategy

The statistician hired by the project will conduct the data analysis for Stage 2 of the study. Descriptive analysis will initially involve means, standard deviation, absolute and relative frequencies. For inferential analysis, either Student's t-tests or Mann-Whitney tests will be employed to compare means based on the distribution and variances of the obtained data. The Fisher's Exact Test will be used for evaluating qualitative variables.

The primary outcome will be assessed concerning the difference in mean scores observed in bronchial asthma control questionnaires (ACT) between groups at each time point through a profile analysis. The secondary outcome will be evaluated based on the proportion of patients adhering to recommendations regarding the correct use of bronchodilators between both groups. Any intra-group comparisons of qualitative data will be conducted using the ANCOVA or Kruskal-Wallis statistic, depending on the distribution of quantitative data.

All analyses will be carried out by a statistician unaware of the treatment assignment of the participants. Outcomes will be analyzed on an intention-to-treat basis (intervention or control group). In the event of an imbalance in the characteristics of the groups established by the randomization process, potential adjustments to the models will be made. Any model generated will consider the presence of potential interactions between independent variables during its design. Maximum likelihood principles will be ensured based on residual analysis.

To preserve the intention-to-treat principles, missing data will be handled using multiple imputation techniques. All analyses will be performed by a masked statistician using R Project software.

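### Inhaler adherence, co-primary in 3.1, becomes a secondary yes/no proportion with no cut-off in 3.4; a checklist score, and Boschloo's test for yes/no data, would usually give more power.

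*Combined protocol and SAP*

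**What the plan says.** **Status.** Section 3.1 lists among the co-primary outcomes, beside the 7- and 30-day ACT differences, "as well as adherence to the recommendations provided by the healthcare team regarding the correct inhalation technique for bronchodilators" and the use of inhalation chambers, over the same time frames. Section 3.4 says: "The secondary outcome will be evaluated based on the proportion of patients adhering to recommendations regarding the correct use of bronchodilators".

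**Instrument.** Section 3.1 has the project clinician assess correct use "according to a checklist developed 10 months after the start of the project". Table I (section 2.3.4) schedules this at t1, t2 and t3, not at t0. Section 3.3 masks the follow-up assessors. The documents do not give the number of items, a scoring rule or the score at which a patient counts as adhering.

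**Tests.** Section 3.4 states: "The Fisher's Exact Test will be used for evaluating qualitative variables". For quantitative data, "either Student's t-tests or Mann-Whitney tests will be employed to compare means", and ACT is compared across time points by a profile analysis. Neither approach is applied to the checklist.

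**Size.** Section 3.2: "we plan to randomize a minimum of 48 patients for Stage 2 of the clinical validation of SIMAP". No power, effect size or test-level alpha is stated, and 3.2 says that a calculation based on effect size was not feasible.

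**The concern.** Two defects are visible in the text alone: the same outcome appears to be co-primary in one section and secondary in another, and the proportion to be compared has no definition.

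A third matter is efficiency. A checklist normally yields a count of steps done correctly. Collapsing the count to yes/no usually loses information, and Fisher's test on small arms loses more because it is conservative. Section 2.3.2 says that the pictograms cover inhalation technique and chamber use, so this outcome lies close to what the intervention teaches. With the sample size set on other grounds, the choice of analysis is one of the few levers left. An effect on technique could be missed for reasons that a change of SAP wording would partly remove.

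**Working it through.** **The plan's own figure.** The only sample-size figure is 48, from a 10% margin of error at 95% confidence. With p = 0.5 (assumed), n0 = 1.96² × 0.25 / 0.10² = 96.04. The finite-population form n0 / (1 + (n0 − 1)/N) gives 48 when N is about 94–95. That population is not stated, so 48 is compatible with the formula but cannot be confirmed. It is a precision figure and says nothing about power for adherence.

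**Inputs.**
- From the documents: 48 patients in two groups. Section 2.3.2 says that blocking "aims to ensure a periodic balance in the number of subjects assigned to each intervention or control group" but gives no ratio.
- Assumed: 24 per arm, two-sided 5%, complete data, a normal latent technique score shifted uniformly by d SD, and a cut-off giving control adherence pc.

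**Formulas.**
- Score: two-sample t-test, 46 degrees of freedom, noncentrality d × √(24/2). For d = 0.8 this is 2.77, and power is 77%.
- Yes/no: intervention adherence is Φ(Φ⁻¹(pc) + d). For pc = 20% and d = 0.8 it is 48%. Fisher's power comes from enumerating all 25 × 25 possible tables; here it is 45%.

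**Results, pc = 20, 30, 40 and 50%** (losses from unrounded powers).

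| d (SD) | Score, t-test | Yes/no, Fisher | Loss (points) |
|---|---|---|---|
| 0.3 | 17% | 7–9% | 9–10 |
| 0.5 | 40% | 17–21% | 19–23 |
| 0.6 | 53% | 25–30% | 24–28 |
| 0.8 | 77% | 45–50% | 28–33 |
| 1.0 | 92% | 64–71% | 22–29 |
| 1.2 | 98% | 79–86% | 12–20 |

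With control adherence of 70–80% the loss over 0.5–1.0 SD is 24–61 points. If dropout leaves 21 or 19 per arm, the loss over 0.5–1.0 SD at 20–50% control adherence is 21–36 or 16–33 points. Against the Pearson z approximation, Fisher's conservatism accounts for about 6–10 points at 0.5–1.0 SD; the rest comes from dichotomising.

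**A discrete score.** A simulation with an assumed 10-item checklist (latent log-odds SD 0.8, 4,000 runs per effect) used log-odds shifts of 0.5, 0.8 and 1.0. Mann-Whitney on the count had 35, 70 and 87% power. Fisher at its best cut-off (at least 7 of 10) had 20, 47 and 67%, a loss of 15–23 points. Fisher on all steps correct had 2, 7 and 15%.

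**Fisher against Boschloo, 24 per arm, same enumeration.** Fisher's maximum true size is 0.0294. Boschloo's test, which here rejects when Fisher's p is at most 0.0798, has maximum size 0.0490.

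| True proportions | Fisher | Boschloo |
|---|---|---|
| 50% v 80% | 49% | 59% |
| 50% v 85% | 67% | 75% |
| 40% v 75% | 62% | 70% |

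**The case against.** **The score does not always win.** The table assumes that the intervention shifts the whole checklist. In an illustrative simulation with 10 items, nine mostly done well and one improving from 40% to 80%, the t-test on total steps had 23% power and Fisher on that one step 77%. With two such steps (50% to 80% each) it was 43% v 72%. This stands. It favours a yes/no rule built on the right steps, though, and the plan names no rule.

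**A proportion is a legitimate, readable summary, and Fisher's test is valid.** Both are true. Conservatism costs power, not validity. Section 3.4 specifies multiple imputation, so Boschloo's test applies directly only where a yes/no outcome is complete.

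**The checklist is not in the documents.** A pass rule may sit in it. That it has several steps, and is recorded item by item, is inferred. Fisher's test is tied to adherence only by inference. One could also read the secondary outcome in 3.4 as something other than the co-primary adherence of 3.1; the co-primary outcome would then have no analysis of its own in 3.4.

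**Stronger readings that the documents do not support.** A reader might infer that the plan discards a known 20 to 30 points of power that the trial already has. No power was calculated, the loss depends wholly on assumed effects and cut-offs, and at 0.5 SD even the score has only about 40%. A reader might also infer that the open cut-off raises false positives to about 10%. That figure needs an assumed 10-step checklist and a search for the best of five cut-offs (7–11% across six assumed score shapes), and the plan keeps the analysing statistician masked. Masking does not replace a fixed definition, but nothing indicates that such a search is planned.

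**Conclusion.** The point holds in a limited form. From the text alone, the status of adherence conflicts between 3.1 and 3.4, and the analysed proportion has no cut-off. The power loss is illustrative: about 19–33 points for effects of 0.5–1.0 SD and about 9–10 points at 0.3 SD. It rests on 24 per arm, two-sided 5%, a uniform shift in a normal latent score and control adherence of 20–50%. It can shrink or reverse if the effect is confined to one or two critical steps. The comparison of Fisher and Boschloo needs fewer assumptions: at 24 per arm with complete data, maximum size is 2.9% against 4.9%, and power differs by about 8–10 points in the three cases computed.

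**What to change.** 1. Provided the checklist is recorded item by item, make the percentage of applicable steps done correctly the tested adherence outcome, so that patients with and without a chamber are comparable. Compare arms in a repeated-measures model over t1 to t3. Report the proportion adhering as supportive, with its definition taken from the checklist and fixed before unmasking. If the checklist shows that the expected effect lies in one or two critical steps, weigh that before adopting an equally weighted score.
2. Where a yes/no outcome with complete data is tested, use Boschloo's exact test in place of Fisher's.
3. Give adherence the same status in 3.4 as in 3.1.

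The cost is SAP wording if item-level data are captured; otherwise the recording form must change too. The downside is that a mean step score is less direct to read than a proportion and weights all steps equally. The proportion is still reported.

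### Multiple imputation is promised, but the Fisher and Mann-Whitney tests named for adherence and possibly ACT give p-values that Rubin's rules cannot pool, and no combining rule is stated

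*Combined protocol and SAP*

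**What the plan says.** All the relevant analysis text is in section 3.4 (Analysis Strategy).

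- Missing data: "To preserve the intention-to-treat principles, missing data will be handled using multiple imputation techniques". No imputation model, number of imputations, missingness assumption or pooling rule follows.
- Quantitative variables: "either Student's t-tests or Mann-Whitney tests will be employed to compare means based on the distribution and variances of the obtained data".
- Qualitative variables: "The Fisher's Exact Test will be used for evaluating qualitative variables". No other between-group test is named for them.
- Primary outcome: the "difference in mean scores observed in bronchial asthma control questionnaires (ACT) between groups at each time point through a profile analysis".
- Adherence: "The secondary outcome will be evaluated based on the proportion of patients adhering to recommendations regarding the correct use of bronchodilators between both groups".

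Section 3.4 calls the adherence comparison secondary. Section 3.1 lists adherence to correct inhalation technique as co-primary, at 7, 30 and 60 days. Section 3.4 also commits to analysis by randomised group and allows model adjustment if the groups are imbalanced. Section 3.2 plans at least 48 randomised patients and states no dropout allowance.

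**The concern.** Multiple imputation produces several completed datasets, and their results must be combined into one. Rubin's rules do this with an effect estimate and its variance from each dataset. Fisher's exact test and Mann-Whitney, as named here, return a p-value from each. With 20 imputations the analyst would hold 20 Fisher p-values for one adherence comparison, some perhaps below 0.05 and some above, and no written way to reach a single answer.

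The ACT analysis has a related weakness. The choice between t-test and Mann-Whitney depends on the distribution of the data, so it could differ between imputed datasets. If it falls on Mann-Whitney, the same pooling gap opens.

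The analyst would have to choose a workaround after the data are in: one imputed set, a median p-value, complete cases, or an effect estimate the plan does not name. These differ in error rate and in which patients they use, and one of the affected outcomes is co-primary.

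**Working it through.** **Which planned analyses pool**

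| Analysis in section 3.4 | Result per imputed dataset | Pools by Rubin's rules? |
|---|---|---|
| ACT mean difference, t-test | difference and variance | Yes |
| Profile analysis of ACT | vector of mean contrasts and covariance | Yes, with a multivariate Wald version for the joint tests |
| Mann-Whitney | p-value | Not as named; its z or the probabilistic index would pool |
| Fisher's exact test | p-value | Not as named; a risk difference or log odds ratio from the same 2×2 table would pool |

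**Inputs**

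The only trial figure used is the minimum of 48 patients (section 3.2). That figure cannot be reproduced, because the population size behind it is not given, but this point does not depend on it. Assumed, because the documents are silent: 1:1 allocation (48 / 2 = 24 per arm), true adherence of 50% in both arms, and data missing completely at random at 15% or 30%.

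**Method for adherence**

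In each simulated null trial, an arm with k observed patients and s adherent has its success probability drawn from Beta(0.5 + s, 0.5 + k − s). Its missing values are drawn from that probability, and this is repeated m times (m = 5 or 20). For the risk difference in each completed dataset:

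- Q = p1 − p0 and U = p1(1 − p1)/24 + p0(1 − p0)/24.
- Total variance T = mean(U) + (1 + 1/m)B, where B is the variance of Q across imputations.
- With λ = (1 + 1/m)B/T and complete-data degrees of freedom 2 × 24 − 2 = 46: ν1 = (m − 1)/λ², ν2 = (47/49) × 46 × (1 − λ), and ν = ν1ν2/(ν1 + ν2).

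**Null rejection at nominal 5%, adherence** (ranges over m and repeated runs)

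| Approach | 15% missing | 30% missing |
|---|---|---|
| Fisher, one imputed set | about 5–6% | 10–11% |
| Median Fisher p-value | 4–6% | 7–9% |
| Rubin-pooled risk difference | 4–6% | 5–6% |
| Fisher, complete cases | 2–4% | 2–4% |

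For reference, Fisher with no missing data rejects in 2.9% of trials at this size. Single runs of 3,000 trials have a Monte Carlo standard error of √(0.06 × 0.94/3000) = 0.4 percentage points; one such run put single-set Fisher at 6.6% with 15% missing. Complete cases leave about 48 × 0.85 = 41 patients at 15% missing and 48 × 0.70 = 34 at 30%.

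**How often the imputed sets disagree**

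At 15% missing, some imputed sets gave Fisher p < 0.05 and others did not in 11% of trials (m = 5) and 16% (m = 20). At 30% missing the figure was about 23–39%. In those trials the conclusion rests on a rule the plan does not contain.

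**ACT**

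A separate null simulation used 24 per arm, m = 20, 1,500 trials, a normal outcome and a correlation of 0.5 with baseline. Its Monte Carlo standard error is about 0.6 percentage points.

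| Approach | 10% missing | 20% missing | 30% missing |
|---|---|---|---|
| Pooled mean difference | 4.8% | 4.0% | 5.9% |
| Pooled Mann-Whitney z | 4.3% | 3.3% | 5.3% |
| Median Mann-Whitney p-value | 5.7% | 6.7% | 9.9% |

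The planned mean difference behaves well once pooled. The drift comes from an improvised rule for Mann-Whitney.

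**The case against.** The strongest reply is that this is missing detail and not a contradiction. Section 3.4 evaluates adherence as a proportion in each group. Two proportions give a risk difference with a variance, and Mann-Whitney has a poolable z and probabilistic index. The section also allows models, so the plan is not confined to bare tests, and the statistician is masked, which limits selective choice. At 15% missing, single-set Fisher at 5–6% is no worse than the pooled risk difference at 4–6%. All of this stands, and it limits the point. It does not remove it: the plan names tests and not those estimates, and masking does not supply a combining rule.

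A reader might infer three stronger things that the documents do not support.

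- *That the intention-to-treat analysis cannot be run.* Intention-to-treat here means analysis by randomised group, which a missing pooling rule does not prevent. The primary ACT mean difference, the t-test and the profile contrasts all pool.
- *That profile analysis will lose every patient with a missed visit.* It would do so on unimputed data, but the plan imputes.
- *That false positives will be grossly inflated because imputed datasets are stacked and analysed as one large sample.* Nothing in the plan proposes stacking.

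**Conclusion.** The point holds in limited form. Multiple imputation is paired with two tests whose p-values Rubin's rules do not combine, and no alternative rule is given. Adherence, other binary outcomes with missing values and any ACT comparison moved to Mann-Whitney are affected. The primary ACT mean difference is not.

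The size depends on how much is missing. At 15% the error rates differ little, and the cost is mainly an undetermined answer when imputed sets disagree. At 30%, workarounds based on Fisher p-values reach 7–11%, against 5–6% for the pooled risk difference. Complete-case Fisher keeps its error rate under these assumptions, but it abandons the promised imputation and drops the patients with missing data.

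The figures rest on assumed 1:1 allocation, 50% adherence and data missing completely at random. They do not carry over to rare events such as hospitalisation, where large-sample methods for proportions are weaker. This should be corrected before analysis, but it is not a fatal flaw.

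**What to change.** Amend section 3.4 as follows.

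- **Binary outcomes with missing values, including adherence at each visit:** replace Fisher with a risk difference (or log odds ratio) and its standard error, estimated in each of at least 20 imputed datasets and pooled by Rubin's rules with small-sample degrees of freedom. Keep Fisher only for outcomes with nothing missing.
- **ACT:** make the day-60 contrast the mean difference adjusted for baseline ACT, which is already collected at t0. Take it either from a likelihood-based repeated-measures model or from the adjusted difference pooled over the imputations. State which, and remove the data-dependent switch to Mann-Whitney.
- **Imputation:** state the variables in the model, the number of imputations and the missingness assumption.

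The cost is revised wording, a few lines of R and slightly more analysis work, with no new data. The trade-off is a large-sample test in place of an exact one for binary outcomes. In the 1,500-trial check at 10%, 20% and 30% missing, the pooled risk difference rejected in 4.4%, 5.7% and 5.6% of null trials, and the pooled log odds ratio (0.5 added to each cell) in 3.4%, 3.9% and 3.6%. The log odds ratio is therefore the more cautious choice, and the risk difference is easier to read.
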